# of patients (in cohort size of 5, starting from the 5th patient)      Stop this cohort if there are this many patients with toxicities:

# of patients ( in cohort size of 5, starting from the 5 th patient)	Stop this cohort if there are this many patients with toxicities:
5	3-5
10	5-10
15	6-15
20	8-20
25	9-25
30	11-30
35	Always stop with this many patients

Table 9. Operating characteristic for toxicity monitoring

True toxicity rate	Prob(stop the trial early)	Average number of patients treated
0.15	0.04	33.87
0.25	0.27	29.02
0.35	0.66	20.46
0.45	0.93	12.94

If patients do not respond to pembrolizumab, they would stop the treatment after two doses. In case the patients have resectable tumors, the subsequent surgical resection will be monitored. Patients will be allowed up to 6 months to have surgery. We expect that 80% of these patients with resectable tumors would undergo surgery. After 5 patients falling into this category, the

Bayesian stopping rule:  $\text{Pr}(\text{surgery rate} > 0.8 | \text{data}) < 0.01$  will be continuously implemented assuming the surgery rate follows a Beta prior (0.8,0.2). That is, if at any time after enrolling 5 patients who have resectable tumor and don't respond to pembrolizumab, we determine that there is a less than 1% chance that the surgery rate is more than 80%, we will stop enrollment of the study. Assuming there are 20 patients, the surgery rate monitoring rule will be applied after the first 5 patients have been enrolled and evaluated, and then will be monitored by cohort of 5. Stopping boundaries corresponding to this stopping rule are listed in Table 10 (operating characteristic in table 11). For example, if there is none or only 1 patient out of the 1st 5 patients undergo surgery, the study will be stopped. Table 10. Early stopping boundaries for surgery rate monitoring for patients who do not respond to pembrolizumab but with resectable tumor

# of patients ( in cohort size of 5, starting from the 5 th patient)	Stop the study if there are this many patients with surgery
5	0-1
10	0-4
15	0-7
20	0-11

Table 11. Operating characteristic for surgery rate monitoring for patients who do not respond to pembrolizumab but with resectable tumor

True surgery rate	Prob(stop the trial early)
0.5	0.56
0.6	0.27
0.7	0.08
0.8	0.01

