## 1.0 TRIAL SUMMARY

Abbreviated Title	Neoadjuvant Pembrolizumab for Patients with Mismatch Repair Deficient Locally Advanced Solid Cancers
Trial Phase	II
Clinical Indication	Treatment of MSI high locally advanced solid tumors in the neoadjuvant setting
Trial Type	Interventional
Type of control	None
Route of administration	Intravenous
Trial Blinding	Unblinded, open-label
Treatment Groups	All patients will receive pembrolizumab 200mg every 3 weeks
Number of trial participants	35 patients
Estimated enrollment period	We estimate that the trial will require approximately 17 months from the first patient enrolling until the final patient signs informed consent.
Estimated duration of trial	We estimate that the trial will require approximately 24 months to allow full accrual and at least the first 6 cycles of pembrolizumab.
Duration of Participation	Until disease progression, drug intolerance, or 24 months of pembrolizumab therapy.
Estimated average length of treatment per patient	One year

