## 2.0 TRIAL DESIGN

### 2.1 Trial Design

This study is a Phase II open-label, single center trial assessing the safety and efficacy of pembrolizumab given pre-operatively for 6 months in patients with locally advanced (unresectable primary cancer or a resectable primary cancer with a high chance of recurrence) dMMR solid organ tumors. High risk will be defined by the treating physician as patients with an estimated risk of recurrence of greater than or equal to 20%. Given the variety of cancer types and variety of factors within each tumor type this decision will be based on an expert treating physician estimation for that specific disease type. As an example, for colon cancer, clinoco-radiographic factors have been incorporated into risk recurrence estimation include: age, CEA level, MRI identified perineural or lymphovascular invasion, radiographic T stage, presence of enlarged lymph nodes on radiographic imaging, and involvement of neighboring structures. Unresectable versus resectable status will be defined at the time of study enrollment, as patients with resectable cancers will be monitored to ensure an adequate rate of surgical resection. All tumor types are eligible and prior radiation or chemotherapy is allowed. Based on epidemiological distribution of dMMR we anticipate 70% of tumors will be colorectal, endometrial, gastric and adrenocortical carcinomas.

To ensure safety, interim safety monitoring will be conducted to ensure the consequent resection in resectable patients who do not respond to therapy. In addition, Bayesian toxicity stopping boundaries will be applied using the approach of Thall, Simon, Estey (1995, 1996) for the total of 35 patients throughout

[figure not shown]
the study. In addition early use of ctDNA will be utilized in addition to radiographic RECIST v1.1 data to help determine treatment benefit at the early time point of 6 weeks. Patients will have pre-treatment and cycle 2 day 1 (3weeks) ctDNA sampling via an MD Anderson CLIA certified 70 gene liquid biopsy panel. After two cycles of pembrolizumab (6weeks) patients will be assessed for a benefit from therapy. Patients with clinical benefit will continue therapy on clinical trial and those that are not benefiting will discontinue the clinical trial. Clinical benefit will be defined if a patient meets any of the following criteria:

- (i) Patients with PR/CR per RECIST v1.1

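### Table 11 treats surgery outcomes as known at once; with the lag to learning of non-surgery, the rule's chance of stopping before enrolment closes is about 0.4, not 0.56, at a true surgery rate of 0.5

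*Combined protocol and SAP*

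**What the plan says.** Section 2.1 (Trial Design): "After two cycles of pembrolizumab (6weeks) patients will be assessed for a benefit from therapy". Section 7.1 adds: "If patients do not respond to pembrolizumab, they would stop the treatment after two doses". For those whose tumours are resectable, later surgery is monitored, and "Patients will be allowed up to 6 months to have surgery". The text does not say when the 6 months begin, or how a patient whose outcome is still pending is counted.

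The rule uses a Beta(0.8, 0.2) prior. It triggers when the posterior probability that the surgery rate exceeds 0.8 falls below 0.01. It first applies once 5 such patients have been enrolled and evaluated, and then by cohorts of 5, on the assumption of 20 such patients. Another sentence in the same paragraph says it runs continuously. The stated action is "we will stop enrollment of the study", but the worked example and the Table 10 header speak of stopping the study.

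Table 10 stops at 0-1 of 5, 0-4 of 10, 0-7 of 15 and 0-11 of 20 operated. Table 11 gives early-stopping probabilities of 0.56, 0.27, 0.08 and 0.01 at true surgery rates of 0.5, 0.6, 0.7 and 0.8.

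Section 1.0 (Trial Summary) plans 35 patients and an enrolment period of "approximately 17 months from the first patient enrolling until the final patient signs informed consent".

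**The concern.** An enrolment-stopping rule protects only patients not yet enrolled when it fires. Stopping at the first look needs at least 4 of 5 patients not operated on, and nothing in Section 7.1 lets a non-surgery count before the window has run out. A lag of 6 to 7.4 months is long against 17 months of accrual, and about 15 further patients enter during it.

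This is the only trial-level stopping rule for resectable patients who lose their operation after an ineffective neoadjuvant course. An IRB or monitoring committee reading Table 11 would credit it with a 56% chance of intervening if only half of these patients reached surgery. If the later looks fall after enrolment ends, that figure is too favourable.

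**Working it through.** **Inputs.** 35 patients over 17 months (Section 1.0); non-response at 6 weeks (Section 2.1); up to 6 months for surgery, prior, threshold, looks and 20 monitored patients (Section 7.1). Assumptions: even accrual, no pause for pending outcomes, looks by cohorts of 5, and non-surgery known only at the end of the window.

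**Step 1: reproduce the plan.** The boundary at n patients is the largest x with Pr(p > 0.8 | Beta(0.8 + x, 0.2 + n − x)) < 0.01. This gives 1, 4, 7 and 11 at n = 5, 10, 15 and 20, which matches Table 10.

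An exact binomial recursion over the looks at 5, 10 and 15, with every outcome known at once, gives 0.559, 0.274, 0.084 and 0.013, which matches Table 11. Counting the look at 20 gives 0.770, 0.442, 0.143 and 0.019, which does not match. Table 11 therefore rests on three looks and no time to outcome.

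**Step 2: the lag.**
- Accrual = 35/17 = 2.06 per month.
- Lag = 42/30.44 + 6 = 7.38 months if the window starts at the week-6 assessment, or 6.0 months if it starts at entry.
- Patients entering during the longer lag = 7.38 × 2.06 = 15.2.

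**Step 3: timing of the looks with 20 monitored patients (f = 20/35).** Month of the look at k patients = (k/f)/2.06 + 7.38.

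| Look | Month | Enrolled | Still to enrol |
|---|---|---|---|
| 5 | 8.75/2.06 + 7.38 = 11.6 | about 24 | about 11 |
| 10 | 17.5/2.06 + 7.38 = 15.9 | about 33 | about 2 |
| 15 | 26.25/2.06 + 7.38 = 20.1 | 35 | 0 |

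Simulation with the monitored patients at random positions among the 35 gives similar results: about 11 to 12 still to enrol at the first look, 3 to 4 at the second, and the third after closure in 98% or more of trials.

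**Step 4: usable stopping probability with 20 monitored patients.** The exact contributions of the looks at 5, 10 and 15 are:
- True rate 0.5: 0.188 + 0.220 + 0.152 = 0.559 (unrounded terms). Without the third look: 0.188 + 0.220 = 0.41.
- True rate 0.6: 0.087 + 0.106 + 0.081 = 0.274. Without the third look: 0.087 + 0.106 = 0.19.

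Simulation, which allows for the second look sometimes also falling after closure, gives about 0.37 to 0.39 at a rate of 0.5, depending on the entry-time convention. With the 6.0-month lag it gives about 0.41 to 0.42. With continuous looks and the full wait it gives about 0.50.

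**Step 5: other numbers of monitored patients, true rate 0.5.**

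| Monitored | First look, month | Stops before closure |
|---|---|---|
| 20 | 11-12 | about 0.4 |
| 10 | 15-16 | about 0.15 |
| 5 | 22-24 | about 0.01-0.03 |

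With the 6.0-month lag the last two become about 0.17 and 0.02. With 5 monitored patients, knowing every outcome at week 6 would raise the figure only to about 0.12.

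**The case against.** Much of the case on the other side stands.

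- A reader might infer that enrolment is always over before the rule can act. The documents do not support that. On the 20 monitored patients that Section 7.1 assumes, the first look leaves about 11 of 35 still to enrol, and 0.41/0.56, or about 73%, of the stated stopping probability remains.
- A reader might also infer that resectable patients have no other protection. They do. Section 6.1.5.2 (Treatment Period) directs any resectable patient with confirmed progression to be evaluated for and proceed to resection, and Section 2.1 ends trial treatment for those not benefiting at 6 weeks. These provisions act on each patient.
- A count of 5 monitored patients can be obtained from Section 7.1 as 35 − 20 − 10. But the 20 and 10 illustrate confidence-interval widths. They do not allocate the 35, and the remainder need not be resectable non-responders. At that count rarity, more than the lag, disables the rule.
- The 7.4 months is one reading. The start of the window is undefined, and a refusal or death might in practice be recorded sooner. Section 7.1 does not say so, however, and the 6.0-month reading changes the result little.
- Continuous looks recover part of the loss (about 0.50). Section 7.1 supports both schedules, but Table 11 was calculated with cohorts.
- The action may be wider than closing enrolment, since two places speak of stopping the study. Even so, a late stop cannot undo doses already given.
- Accrual slower than the approximate 17 months would weaken the point.

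**Conclusion.** The concern holds in this limited form: Table 11 overstates what the rule can do before enrolment closes, because it ignores the time needed to learn that surgery did not take place. With the plan's own 20 monitored patients, the chance of stopping before closure is about 0.4 rather than 0.56 at a true surgery rate of 0.5, and about 0.19 rather than 0.27 at 0.6. The first look remains useful, the second comes late, and the third is too late.

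The number of resectable non-responders is otherwise not given. With 10 the figure at a rate of 0.5 is about 0.15; with 5 the rule almost never acts before closure, largely because such patients are rare. The results assume even accrual over 17 months, no accrual pause, looks by cohorts of 5 and non-surgery scored at the end of the window. The overstatement remains under either reading of the window's start.

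**What to change.** In Section 7.1:

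1. State when the 6-month window starts. Count a patient as a non-surgery on the date surgery is documented as declined or no longer possible, or on metastasis precluding surgery or death, and otherwise at the end of the window. If failures became known 0.5 to 3 months after week 6 (an assumption), stopping before closure with 20 monitored patients at a true rate of 0.5 would rise from about 0.39-0.40 to about 0.54.
2. Recompute Table 11 with the outcome lag, the planned accrual and a plausible range of monitored patients (for example 5 to 20), and give the expected number enrolled at each look.
3. Reconcile stopping enrolment with stopping the study, and continuous monitoring with cohorts of 5.

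The 6 months allowed for surgery need not change. The cost is SAP wording, one rerun of the operating characteristics, slightly less favourable stated stopping probabilities, and prompt recording of surgical status for a few patients.

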## 7.2 Statistical Analysis Plan

Analysis Plan:

All patients who received any dose of the study agent, pembrolizumab, will be included in the analysis for efficacy and safety. Demographic/clinical characteristics and safety data of the patients will be summarized using descriptive statistics such as frequency, mean, standard

deviation, median and range. We will follow standard reporting guidelines for adverse events. Safety data will be summarized by category, severity and frequency.

Safety will be recorded according to CTCAE toxicity and also post-operative complications will be classified according to Clavien-Dindo classification.

For the efficacy analysis, we will estimate the pathological complete response and rate of organ sparing at 1 year along with the 95% confidence interval.

For each subject, relapse-free survival and overall survival will be calculated. Relapse-free survival is defined as the number of days from the date of response to the date of documented treatment failure, relapses or death from any cause, whichever occurs first, and will be calculated for all patients. The overall survival is defined as the time from treatment start till death or last follow-up. The distribution of time-to-event endpoints including overall survival (OS) and event free survival (RFS) will be estimated using the method of Kaplan and Meier. Comparisons of time-to-event endpoints by important subgroups will be made using the log-rank tests. The association between response (e.g. pathological complete response) and patient's clinical characteristics, such as changes in ct DNA, mutation burden, T-effector cell populations, gene expression profiles, etc. will be examined by Wilcoxon's rank sum test or Fisher's exact test, as appropriate.

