## 2.4 Secondary Objective

- (i) To quantify the rate of organ sparing at 1 year for all patients treated with one dose of pembrolizumab (intent to treat) and those patients who receive at least 3 doses of neoadjuvant pembrolizumab and decline to undergo surgical resection and opt to continue receiving pembrolizumab for a total of 1 year.
- (ii) To assess radiographic tumor response to neoadjuvant pembrolizumab
- (iii) To estimate the relapse-free survival and overall survival in all enrolled participants
- (iv) To determine the overall rates of pathological response to neoadjuvant pembrolizumab
- (v) To assess the rate of complete pathological response (intent to treat) for patients who undergo surgical resection following at least 1 dose of neoadjuvant pembrolizumab.

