## **7.0 STATISTICAL ANALYSIS PLAN**

### **7.1 Statistical Analysis Plan Summary**

Statistical Consideration:

Efficacy:

- 1) The primary endpoint is Pathological complete response ([pCR](#)) after 3 doses. Pathological complete response will also be estimated for all patients who receive at least 1 dose of pembrolizumab (intent to treat). Those who do not undergo surgical resection will be classified as non-pCR for the intention to treat analysis. We will estimate the pCR rate among the group of patients who receive at least 3 doses of pembrolizumab and undergo surgical resection (the primary endpoint). Assuming the pCR is 80%, with 20 patients, the 95% confidence interval is (0.56, 0.94).
  
- 2) Rate of organ sparing at 1 year (primary tumor control and no metastatic disease) will be assessed for all patients who receive at least 1 doses of neoadjuvant pembrolizumab for the intention to treat analysis. In addition we will estimate the organ sparing rate at 1 year among the group of patients who receive at least 3 doses of neoadjuvant pembrolizumab and do not undergo surgical resection. Assuming the organ sparing rate of 0.7, with 10 patients, the 95% confidence interval is (0.35, 0.93) .

Safety monitoring:

Toxicity will be monitored using the Bayesian approach of Thall, Simon, Estey (1995, 1996) and the extension by Thall and Sung (1998). Multc Lean Desktop (version 2.1) was used to generate the stopping boundaries and the OC tables for toxicity monitoring. Toxicity monitoring will be performed (n=35 patients) throughout the study. Unacceptable toxicities are defined as any Grade 3 or higher probably or definite treatment-related CTCAE toxicity that occurs during the first 6 months of therapy. Denote the probability of toxicity by PT. We assume as a priori,  $PT \sim \text{beta}(0.5, 1.5)$ . Our stopping rule is given by the following probability statement:

$$\Pr(PT > 0.25 | \text{data}) > 0.85.$$

That is, we will stop the trial for new patient enrollment if at any time during the study, we determine that there is more than 85% chance that the unacceptable toxicity rate is more than 25%. This toxicity monitoring rule will be applied after the first 5 patients have been enrolled and evaluated, and then will be monitored by cohort of 5. Stopping boundaries corresponding to this stopping rule are listed in Table 8.

Table 8. Early stopping boundaries for toxicity monitoring

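### Relapse-free survival counts from an undefined date of response yet is required for every patient, so patients who never respond have no start date

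*Combined protocol and SAP*

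**What the plan says.** Section 7.2 gives the rule in a single sentence: "Relapse-free survival is defined as the number of days from the date of response to the date of documented treatment failure", or to relapse or death from any cause, "whichever occurs first, and will be calculated for all patients". The sentence before it also asks for RFS and overall survival (OS) for every subject.

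The population is set in two places:

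- Section 7.2, analysis set: "All patients who received any dose of the study agent, pembrolizumab, will be included in the analysis for efficacy and safety".
- Section 2.4(iii), objective: "To estimate the relapse-free survival and overall survival in all enrolled participants".

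OS, in the same paragraph, has a different origin: "The overall survival is defined as the time from treatment start till death or last follow-up". Both endpoints go into Kaplan-Meier estimates and subgroup log-rank tests. At that point the abbreviation RFS is attached to the term event-free survival.

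No section defines response for the purpose of RFS. The word appears in these senses:

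- **Section 7.2**, on biomarker associations: "The association between response (e.g. pathological complete response". Here pCR is only an example.
- **Section 6.1.2.6.4** makes RECIST 1.1 the main measure of tumour response and of the progression date. Section 6.1.2.6.1 (Tumor Imaging During the Study) asks for PR or CR to be confirmed at least 4 weeks later.
- **Section 2.5(iv)**, an exploratory gene-expression comparison, counts stable disease with radiographic response and treats progression before resection as non-response.

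Section 7.1 expects some patients not to respond. They stop after two doses, and those with resectable tumours have their own surgery-rate stopping rule.

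**The concern.** A time-to-event endpoint needs an origin that every member of its population has. A date of response exists only for responders, whereas the same sentence asks for the endpoint in everyone. The two halves of the sentence cannot both be carried out.

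The likely shortcut is to analyse whoever has a response date. The Kaplan-Meier curve would then be a duration of response. It would leave out failures and deaths that occur before or without response, and it would not answer objective 2.4(iii). The trial is open-label with one arm, so leaving the origin to be chosen once outcomes are known also gives the analyst a choice that an SAP is meant to remove. The planned subgroup log-rank tests would inherit the same gap.

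**Working it through.** **Step 1. Does any reading of response give everyone a start date?**

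- *RECIST 1.1 response:* patients whose best result is stable disease or progression have no date. For responders, the plan does not say whether the first scan or the confirming scan counts.
- *pCR:* resected patients with residual tumour and all unresected patients have no date. Section 7.1 classes the unresected as non-pCR in its intention-to-treat pCR analysis; RFS has no matching rule.
- *The Section 2.5(iv) grouping:* patients who progress before resection have no date. Section 6.1.5.2 provides for such patients by sending resectable ones with confirmed progression to surgery. Stable disease also has no natural response date.

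Each reading leaves some treated patients without an origin, so the contradiction does not depend on which is chosen.

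**Step 2. Inputs for an illustration, taking response as pCR.** The total is 35 patients (Sections 1.0 and 7.1). Section 7.1 has two precision examples: "Assuming the pCR is 80%, with 20 patients, the 95% confidence interval is (0.56, 0.94") and "Assuming the organ sparing rate of 0.7, with 10 patients".

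**Step 3. Reproduce the plan's figures.** Exact (Clopper-Pearson) 95% intervals:

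- 0.80 × 20 = 16; 16/20 gives (0.563, 0.943), matching the stated (0.56, 0.94).
- 0.7 × 10 = 7; 7/10 gives (0.348, 0.933), matching the stated (0.35, 0.93).

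**Step 4. Count patients without a start date.**

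- With pCR: 16. Without: 35 − 16 = 19, and 19/35 = 54%.
- Make-up of the 19: 20 − 16 = 4 resected without pCR; 10 unresected; 35 − 20 − 10 = 5 in neither example.
- The 5 might include pCRs, since objective 2.4(v) counts pCR after as little as one dose. If k of them had pCR, the count is 19 − k: from 18 (51%) at k = 1 to 14 (40%) at k = 5.
- The 19 are not all failures. The second example assumes 7 of its 10 unresected patients are organ-spared at 1 year, and they too would have no RFS.

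**Step 5. Same count with first dose as origin.** Every treated patient has a first dose, so 0 of 35 lack a start date.

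**The case against.** The best defence is that a competent statistician would see the problem and either start the clock at treatment, as OS does, or read all patients as all responders. Neither rescues the text. The paragraph uses treatment start for OS and then writes something different for RFS. The responders-only reading conflicts with the instruction to calculate RFS for every subject and with objective 2.4(iii).

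Several further objections stand, and they rule out stronger readings that a reader might infer:

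- **That the plan expects 19 of 35 patients to have no RFS.** It does not. The 20 and the 10 are sizes chosen for two separate precision examples, not a planned split of the 35, and the group of 5 is only a remainder.
- **That the response rates in Section 3.1 size the problem under RECIST.** The 71% and 40% are immune-related response rates and the 31% is for nivolumab, all in metastatic disease. They do not give a RECIST 1.1 rate for this trial.
- **That response has many rival definitions.** The 6-week clinical-benefit rule in Section 2.1 governs continuation of treatment and is not a definition of response. The ambiguity is chiefly RECIST 1.1 response against pCR, with Section 2.5(iv) as a separate grouping.
- **That the plan prescribes a responders-only curve.** It prescribes two incompatible things. The responders-only curve is one way out of them, and the bias follows only if that way is taken.

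RFS is also secondary, with no power calculation or decision attached.

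**Conclusion.** The definition is wrong as written: RFS cannot be computed for the population that Sections 2.4(iii) and 7.2 name. That rests on the text alone and needs no numerical assumption.

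A responders-only analysis would probably look too favourable for the treated population, because early failures drop out. The documents do not allow the bias to be sized. The direction is likely but not certain: under the pCR reading some omitted patients may be doing well, and a later origin shortens each responder's recorded time.

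The figure of about 19 of 35 (14 to 18 if one to five of the unplaced patients had pCR) is an illustration. It assumes that all 35 are treated, that response means pCR, and that the example sizes apply. The pCR, organ-sparing and OS analyses and both stopping rules are unaffected. This should be fixed before analysis, but it does not threaten the primary result.

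**What to change.** Revise Section 7.2 before analysis:

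1. **Origin and population.** Start the all-patient endpoint at first dose, as OS does, in everyone who received at least one dose. State that this treated set is the one used for objective 2.4(iii), whose wording refers to enrolled participants.
2. **Events and censoring.** Run to the first of progression, treatment failure, relapse after resection, or death from any cause. Define treatment failure, which is undefined at present. Censor patients without an event at the last disease assessment.
3. **One name.** Use a single label, since the paragraph now uses both relapse-free and event-free survival. With first dose as origin this is an event-free type of endpoint, a design choice that the SAP should state openly.
4. **Progression date.** RECIST 1.1 dating cannot be taken as settled. Reconcile Section 6.1.2.6.4 (RECIST 1.1 for the progression date) with Sections 6.1.2.6, 6.1.2.6.1 and 6.1.2.6.5 (iRECIST confirmation), and say whether the first or the confirmed date counts. Say also how events are dated in patients with disease that is not RECIST-measurable, whom Section 2.1 may admit.
5. **Response-anchored interval.** If kept, report it separately as duration of response in responders, with response and its date defined.

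The cost is a short SAP revision, with no added patients or visits. The Post-Treatment Visits text already plans chart review or calls about every six months, for up to 2 years, for survival and recurrence, and does not limit this to responders. The SAP should confirm that this covers patients whom Section 2.1 takes off the trial at 6 weeks. The reported figure may be less favourable.

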## 2.5 Exploratory Objective:

- (i) To explore the predictive ability of changes in ctDNA for efficacy endpoints.
- (ii) To determine if total mutational burden correlate with response and extent of benefit from pembrolizumab
- (iii) To correlate pre-treatment tumor samples tumor-immune microenvironment (for example T-effector cell populations; CD4 subsets; T-regulatory populations; B cell populations; dendritic and macrophage populations) with efficacy endpoints.
- (iv) To compare targeted gene expression profiles of immune related genes and genes pertaining to common cancer signaling pathways in pre-treatment samples and also the change in these factors for cases with both pre and on-treatment (i.e. at time of resection) tumor samples of responders (stable disease or radiographic response prior to resection) versus non-responders (progression prior to resection).

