## IMMUNOTHERAPY IN METASTATIC dMMR CANCER

Mismatch-repair deficiency (dMMR) occurs in a number of solid cancers including colorectal, endometrial, gastric, uterine, biliary tract, pancreatic, ovarian and small intestinal cancer, with 70% of cases occurring among the first three. Key studies have shown that mismatch-repair status predicts clinical

benefit of immune checkpoint blockade. In a landmark trial to assess the clinical activity of pembrolizumab in patients with progressive metastatic carcinoma with and without mismatch-repair deficiency, Le et al showed immune-related objective response rate and immune-related progression free survival rate of 71% and 67% in patients with mismatch-repair deficient non-colorectal cancers. The immune-related objective response rate and immune-related progression free survival rates for mismatch deficient colorectal cancers were 40% and 78% respectively compared to 0% and 11% respectively for mismatch-repair proficient colorectal cancers (see figures 2 and 3 below).

**Figure 3.** Radiographic responses to treatment with pembrolizumab based on RECIST criteria.

**Figure 4.** Overall survival among patients with patients with mismatch repair deficient and proficient CRC after pembrolizumab.

Our group has similarly shown high response rates of 31% and progression free survival of 69% at 12 weeks or more in patients with metastatic colorectal cancer with dMMR, treated with nivolumab. Median duration of response was not yet reached at median follow up of one year.

This activity level has also been demonstrated by Le et al as the pembrolizumab study for dMMR solid tumors provided therapy for a maximum of 2 years. At the time of the publication 18 patients had reached 2 years and stopped therapy. At a median follow-up of 8 months, none of these 18 patients has had disease progression/recurrence.

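### The exploratory marker-response tests pool all tumour types without stratification, so a marker that differs by tumour type may appear associated with response if response also differs by type

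*Combined protocol and SAP*

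**What the plan says.** Section 7.2 describes the marker analyses in one sentence. It covers "The association between response (e.g. pathological complete response) and patient's clinical characteristics, such as changes in ct DNA, mutation burden, T-effector cell populations, gene expression" and similar items, which "will be examined by Wilcoxon's rank sum test or Fisher's exact test, as appropriate". No stratification factor, covariate, significance level or multiplicity rule is given. The only subgroup provision in 7.2 is a log-rank comparison by unnamed subgroups, and it applies to time-to-event endpoints.

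The population is mixed by design. Section 2.1 states "All tumor types are eligible and prior radiation or chemotherapy is allowed" and adds that "we anticipate 70% of tumors will be colorectal, endometrial, gastric and adrenocortical carcinomas". The colorectal share alone is not stated.

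The background section on immunotherapy in metastatic dMMR cancer reports that a pembrolizumab trial "showed immune-related objective response rate and immune-related progression free survival rate of 71% and 67% in patients with mismatch-repair deficient non-colorectal cancers", while the corresponding rates for "mismatch deficient colorectal cancers were 40% and 78% respectively".

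Section 2.5 lists the marker objectives as exploratory. Objective (iv) compares "targeted gene expression profiles of immune related genes and genes pertaining to common cancer signaling pathways" between responders, defined as stable disease or radiographic response before resection, and patients who progressed.

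**The concern.** A two-group test over all patients asks whether the marker differs between responders and non-responders. If tumour type is related to both the marker and the response, the answer can be yes even when the marker carries no information within any tumour type. Section 2.5 asks what predicts or correlates with benefit from pembrolizumab. A tissue-of-origin signature reported as an answer could steer later marker selection wrongly. Expression and immune-infiltrate markers are plausible candidates for differing by tissue, although the documents do not say that they do.

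A second, separate gap is that objective 2.5(iv) involves many genes and 7.2 does not say how the number of tests will be handled.

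**Working it through.** **Plan's own figure.** No figure is stated for the marker tests. The nearest is the interval in 7.1 for a pCR of 80% with 20 patients. The exact (Clopper-Pearson) interval for x=16, n=20 has lower limit Beta(0.025; 16, 5) = 0.563 and upper limit Beta(0.975; 17, 4) = 0.943. This matches the stated (0.56, 0.94). It also shows that the plan uses one pCR rate for all tumour types and about 20 patients for pCR.

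**Inputs from the documents.** N=35 enrolled and N=20 resected; response 40% colorectal and 71% other, or alternatively 78% and 67%; a common pCR of 80%.

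**Assumptions.** Two-sided 5% level (none is stated); non-colorectal share 30 to 50%; a normally distributed marker shifted by d = 0.5 to 2 SD between the two groups and unrelated to response within each.

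**Mechanism, by hand, with equal shares.**
- 40%/71%: overall response is 0.5×0.40 + 0.5×0.71 = 0.555. The non-colorectal share is 0.355/0.555 = 0.64 among responders and 0.145/0.445 = 0.33 among non-responders. The marker means therefore differ by about 0.31×d.
- 78%/67%: overall response is 0.725. The shares are 0.335/0.725 = 0.46 and 0.165/0.275 = 0.60. The means differ by about −0.14×d, which is smaller and in the opposite direction.
- Equal rates: the difference is zero.

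**Tests compared by simulation.** W is the rank sum of the a responders, and b is the number of non-responders.
- Pooled Wilcoxon: z = (W − a(N+1)/2) / √(ab(N+1)/12), with continuity correction.
- van Elteren: z = Σ wₖ(Wₖ − aₖ(nₖ+1)/2) / √(Σ wₖ² aₖbₖ(nₖ+1)/12), with wₖ = 1/(nₖ+1) and strata colorectal and other.

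False-positive rate under 40%/71%:

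| N | Colorectal / other | Pooled, 0.5 SD | Pooled, 1 SD | Pooled, 2 SD | Stratified, all shifts |
|---|---|---|---|---|---|
| 35 | 18 / 17 | 7% | 12.6% | 25.6% | 4–5% |
| 35 | 24 / 11 | 6% | 11.1% | 20.9% | 5–6% |
| 20 | 10 / 10 | about 6% | 8.5% | 16.1% | 4–5% |
| 20 | 14 / 6 | about 6% | 6.7% | 12.4% | about 5% |

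With 3,000 runs per cell (the 1 and 2 SD columns) the Monte Carlo standard error is √(0.05×0.95/3000) = 0.4 points near 5%, and 0.8 points near 25%.

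The same pooled test under other response patterns:
- 78%/67%: about 5 to 8% at N=35 and 4 to 6% at N=20.
- 80% in both groups: 3 to 5%.
- pCR 75%/85% (assumed): 4 to 5% at N=20; 5 to 7% at N=35 for 1 to 2 SD.

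**Extreme case.** For a binary marker identical to tumour type under 40%/71%, with a colorectal share of 30 to 70%, the exact Fisher rejection probability is 13 to 22% at N=20 and 30 to 42% at N=35. With a common rate of 55% it is 1.3 to 4.0%.

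**Gene panel.** Its size is not given. At an unadjusted 5%, an assumed 50 genes with no effect give 0.05×50 = 2.5 chance findings, and 750 give 0.05×750 = 37.5.

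**The case against.** The premise is thin. The 71%/40% contrast is one comparison of immune-related objective response in metastatic disease, without group sizes, and the progression-free rates reported with it point the other way. The response named as the example in 7.2 is pCR. The documents give no pCR contrast by type; the only dMMR pCR data quoted are seven colon cancers on a different regimen. For objective 2.5(iv) responders include stable disease, so an objective response rate does not describe that comparison either. With the progression-free rates as a rough proxy, the inflation nearly vanishes. The marker shift and the tumour mix are both assumed. Marker numbers may fall short of 35, because about 20 resected patients are foreseen for pCR and tumour biopsies are optional. Nothing confirmatory hangs on these tests, and simple unadjusted tests are defensible at this size.

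Most of this stands, and it limits the size and priority of the point. It does not remove it. Section 7.2 gives pCR only as an example of response, and radiographic response is itself a secondary objective in 2.4(ii). Nothing in the plan would let a reader tell a tissue signature from a within-type association.

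A reader might infer that the documents show response to differ by tumour type, and that such a marker will appear predictive. Neither follows. For pCR the difference is only an assumption, and even under 40%/71% a false finding remains less likely than not in every setting examined.

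**Conclusion.** The gap is real but modest. The planned tests can confound marker with tumour type, and 7.2 contains no safeguard. If response differs by type as 40% versus 71%, the false-positive rate at a nominal 5% is about 6 to 26% at N=35 and 6 to 16% at N=20, for assumed shifts of 0.5 to 2 SD and a non-colorectal share of 30 to 50%. If response follows 78%/67% or is equal across types, it stays at about 8% or less. The documents cannot settle which pattern applies to pCR. The stratified test holds close to 5% throughout. The analyses are exploratory and the primary pCR estimate is untouched, so this is an improvement to consider rather than a required correction.

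**What to change.** In 7.2, keep the Wilcoxon and Fisher tests and label their results as unadjusted for tumour type. Report beside each the version stratified by colorectal versus other: van Elteren for continuous markers, exact Cochran-Mantel-Haenszel for binary ones. State that a marker will be described as associated with response beyond tumour type only if the stratified result supports it. For the gene panel of objective 2.5(iv), state the number of genes and report Benjamini-Hochberg adjusted values at a 10% false discovery rate.

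The change is to wording only, since the diagnosis is already recorded for eligibility. The stratified test is less powerful for a marker that does not differ by type. For a 1 SD effect under 40%/71%, power falls from about 77% to 70% at N=35 and from about 51% to 42% at N=20. When type does not predict response, the loss is about 2 to 4 points. This is why the stratified test should be added rather than substituted. Two strata leave confounding within the other group, but with 20 to 35 patients finer strata would be too sparse.
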